3.11. Visit Windows

It is expected that all visits should occur according to the protocol schedule. All data will be tabulated per the evaluation visit as recorded on the eCRF even if the assessment is outside of the visit window. In data listings, the relative day of all dates will be presented (see [Section 3.2](#)).

3.12. Timing of Analysis

Efficacy data were not summarized at that time. The respective analyses were described in a separate Statistical Analysis Plan.

There were no planned interim efficacy analyses. The Final, End of Study Analysis in support of the CSR will be supported from the analyses described in this document.

4. STUDY ANALYSES

4.1. Patient Disposition

Patient disposition will be tabulated and include the number screened, the number treated in total, the number in each patient population for analysis, the number treated in each Stage of the study, the number who withdrew prior to completing the study and reason(s) for withdrawal. The summary will be presented by dose level and stage.

A data listing of study completion information, including the reason for premature study withdrawal, if applicable, will be presented.

4.2. Demographics and Baseline Characteristics

Demographics and baseline characteristics will be summarized and presented by dose level and Stage. Age, height, and weight will be summarized using descriptive statistics (number of patients, mean, SD, median, minimum, and maximum). The number and percentage of patients in each gender, ethnicity, race, and ECOG performance status category will be presented.

Medical history and results from baseline screens such as for pregnancy, and smoking history will be tabulated. Primary disease history will be summarized including CD123 status, AML baseline diagnosis, time since AML diagnosis, and adverse-risk AML and MRD disease elements. Prior radiotherapy and prior systemic therapy (for AML and not related to AML) will be summarized.

Demographic and baseline data for each patient will be provided in data listings.

4.3. Efficacy Evaluation

Data for all efficacy endpoints will be presented in by-patient listings. Subgroup analyses for all efficacy outcomes will be presented by MRD Status and line of therapy.

4.3.1. Eradication (Conversion) of MRD

The rate of MRD eradication (conversion) will be presented as the number and percentage of patients with evidence of MRD prior to initial treatment with Tagraxofusp for whom MRD cannot be detected upon subsequent assessments.

Rates of MRD eradication at a single assessment and at multiple time points following initiation of Tagraxofusp will be presented.

95% Clopper Exact CIs will be presented for each rate.

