5.2 Patient Inclusion Criteria

To be included in the study, a patient must meet the following criteria:

1. The patient has a diagnosis of AML according to WHO criteria.
2. The patient received any induction chemotherapy regimen and may have received post-remission consolidation therapy prior to screening.
3. The patient achieved a first or second CR or CRi. For patients without evidence of MRD in CR/CRi, CR (or CRi) must have been initially identified within 12 months prior to screening.

OR

The patient has achieved first or second CR or CRI with evidence of MRD at least 6 months post stem cell transplant without evidence of acute or chronic graft-versus-host disease post-transplant and has not received immunosuppressant therapy for at least 14 days prior to SL-401 therapy.

4. The patient has adverse risk disease or AML for which there is otherwise a substantial risk of relapse, which includes but is not limited to: adverse karyotype, FLT3 internal tandem duplication (ITD) mutation, history of antecedent hematologic disorder (AHD), therapy-related AML, history of requiring more than 1 cycle of intensive induction chemotherapy to achieve first remission, and/or presence of persistent MRD (detected by cytogenetics, molecular markers, or flow cytometry) at any point after the initial induction cycle. (A more comprehensive listing of karyotypes and mutations indicative of high-risk AML is provided as an appendix to the protocol [Section [15.3](#) Appendix C]).
5. For patients enrolling in Stage 2, the bone marrow evaluation determined locally within the previous 6 months indicates the presence of MRD. (A more comprehensive listing of methodologies for evaluation of MRD is provided as an appendix to the protocol [Section [15.4](#) Appendix D]).
6. The patient is not considered to be an immediate candidate for allogeneic stem cell transplant as determined by the investigator.
7. The patient is ≥ 18 years old.
8. The patient has an Eastern Cooperative Oncology Group (ECOG) performance status (PS) of 0-2.
9. The patient has adequate baseline organ function, including cardiac, renal, and hepatic function:
 - Left ventricular ejection fraction (LVEF) \geq institutional lower limit of normal as measured by multigated acquisition scan (MUGA) scan or 2-dimensional (2-D) echocardiogram (ECHO) within 28 days prior to start of therapy and no clinically significant abnormalities on a 12-lead electrocardiogram (ECG)
 - Serum creatinine ≤ 1.5 mg/dL

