6.2.2 Stage 2: Expansion

During Stage 2, up to 20 additional patients with evidence of MRD as determined locally will be treated at the MTD or maximum tested dose at which multiple DLTs are not observed (identified in Stage 1) so that up to 15 patients with evidence of MRD as determined centrally are evaluable for safety and response at this dose. For inclusion in the study, all patients treated in the expansion phase should have MRD in bone marrow, as determined locally, via at least one of the following modalities: multi-parametric flow cytometry, cytogenetic evaluation, FISH, real-time PCR, or next-generation gene sequencing. It is anticipated that at approximately 50% of patients evaluated with AML in first remission (CR or CRi) will have evidence of MRD.

6.2.3 Tumor Assessments during Stages 1 and 2

All patients must have a baseline (pre-treatment) bone marrow aspirate (+ biopsy) and peripheral blood sample within 14 days prior to the first administration of SL-401. Subsequent assessments will be performed on the following schedules until, in the judgment of the Investigator, there is evidence of relapsed or progressive disease:

- Bone marrow aspirates (+ biopsy) and peripheral blood samples 28 (\pm 7) days after the start of Cycles 2, 4 and 6, then every 3 months (\pm 1 month) until Month 12. No repeat bone marrow is necessary if non-response or progressive disease can be unequivocally diagnosed from peripheral blood tests.
- If the Cycle 2 (Day 28 [\pm 7]) bone marrow examination is empty (i.e., hypocellular) or inadequate, a bone marrow examination should be repeated in 14 (\pm 7) days to document response. If additional time is required to complete the repeat examination, consult with the Medical Monitor.
- Bone marrow will be assessed for morphologic evidence of AML recurrence, and flow cytometric and other cytogenetic/molecular assessments, including evaluation of MRD.
- CD123 is to be assessed in all bone marrow samples (and, if applicable, tissue samples) by flow cytometry (i.e., CD123 should be added to the panel of markers assessed by flow cytometry of bone marrow aspirates) and immunohistochemistry and the results recorded and captured in the electronic case report form (eCRF). (The Cycle 2, 4, and 6, Day 28 [\pm 7 days] peripheral blood and bone marrow assessment should occur on Day 28 [\pm 7 days] even in the setting of patients receiving SL-401 over 6-10 days [as opposed to 5 consecutive days]).

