7.6.2 Procedures and Follow-up after Treatment Discontinuation

The evaluation during which the Investigator determines that SL-401 will be discontinued should be considered the End of Treatment Evaluation; all tests and procedures for the End of Treatment Evaluation are listed in [Table 6](#). In addition, patients should be followed for a minimum of 30 days after the last infusion of SL-401 for assessment of AEs (including potential new AEs and potential change/resolution of existing AEs).

If the patient is in CR/PR at the time of discontinuation, tumor assessments should continue to be performed as described in Section [8.11](#) until, in the judgment of the Investigator, there is evidence of relapsed or progressive disease. Beyond the End of Treatment Evaluation and 30-day follow up (safety/AE assessment), it is requested that subsequent follow-up occur approximately every 90 days for ascertainment of survival status.

If the patient discontinues SL-401 treatment and also withdraws consent for collection of future information, no further evaluations should be performed and no additional data should be collected as part of the study. The Sponsor will only retain and use any data collected before withdrawal of consent.

Please consult Section [6.4](#) for recommendations concerning ongoing follow-up of patients alive with or without evidence of disease progression at the time of Study Completion/assessment of primary and critical secondary endpoints.

8 Study Procedures

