11.2 Determination of Sample Size

The primary objectives of the study are to determine the MTD or the maximum tested dose where multiple DLTs are not observed (Stage 1), and to further characterize the safety profile of SL-401 at this dose (Stages 1 and 2). The anticipated sample size is sufficient to evaluate these objectives.

A secondary objective is to characterize the anti-tumor activity of SL-401. In Stage 2, up to 20 additional patients with MRD as determined locally will enroll and receive SL-401 at either the MTD or maximum tested dose, so that a total of 15 patients with evidence of MRD, as determined centrally, are treated at this dose. The assumptions governing sample size are as follows:

- Null hypothesis: eradication of MRD $\leq 5\%$
- Alternate hypothesis: eradication of MRD $\geq 20\%$
- Type 1 error: 17% one-sided
- Power: $>80\%$

Because no available anti-leukemia therapies (other than allogeneic transplant) are believed to be associated with the eradication of evidence of MRD in this high-risk AML setting, the study

would be considered positive if ≥ 2 of 15 patients in 1st remission (CR) are converted from MRD-positive to MRD-negative status. (In a situation where 1 of 15 patients has eradication of MRD, the results may be considered of interest, given the dearth of efficacious therapy in this setting).

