3. GENERAL STATISTICAL METHODS

3.1. Sample Size Justification

Approximately 21-33 adult patients diagnosed with AML that is considered high-risk disease who have achieved a first or second CR or complete remission with incomplete bone marrow recovery (CRi) within 6 months prior to enrollment and are not considered immediate candidates for allogenic stem cell transplant (SCT). The anticipated sample size is sufficient to evaluate the primary objectives.

During Stage 1, approximately 9-18 patients will be treated with Tagraxofusp.

In Stage 2, up to 20 additional patients with MRD as determined locally will enroll and receive Tagraxofusp at either the MTD or maximum tested dose, so that a total of 15 patients with evidence of MRD, as determined centrally, are treated at this dose. The assumptions governing sample size are as follows:

- Null hypothesis: eradication of MRD $\leq 5\%$
- Alternate hypothesis: eradication of MRD $\geq 20\%$
- Type 1 error: 17% one-sided
- Power: $>80\%$

Because no available anti-leukemia therapies (other than allogeneic transplant) are believed to be associated with the eradication of evidence of MRD in this high-risk AML setting, the study would be considered positive if ≥ 2 of 15 patients in 1st remission are converted from MRD-positive to MRD-negative status. (In a situation where 1 of 15 patients has eradication of MRD, the results may be considered of interest, given the dearth of efficacious therapy in this setting).

At the time of database lock, in Stage 1, 18 patients were enrolled. In Stage 2, 9 patients with MRD were enrolled.

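### The MRD eradication endpoint has no cut-off at transplant and does not name the central baseline, so a marrow cleared by transplant would count as an SL-401 conversion under a rule that needs only two events

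*SAP*

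**What the plan says.** **Endpoint.** SAP 4.3.1 counts "patients with evidence of MRD prior to initial treatment with Tagraxofusp for whom MRD cannot be detected upon subsequent assessments". Protocol 11.5.1 has the same structure and explicitly includes post-treatment assessments. Neither has a rule for marrows taken after stem cell transplant (SCT) or another anti-leukemia therapy.

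**Test.** SAP 3.2 makes MRD eradication in Stage 2 the only endpoint with formal hypothesis testing. SAP 3.1 and Protocol 11.2 set a null rate of 5%, an alternative of 20%, "Type 1 error: 17% one-sided" and power above 80%. The study is called positive at 2 or more conversions in 15 patients.

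**Follow-up.** Protocol 7.6.2: "If the patient is in CR/PR at the time of discontinuation, tumor assessments should continue to be performed". Protocol 8.11.1 schedules marrows through 12 months from the start of SL-401, then at the investigator's discretion. Protocol 7.4 bars other anti-leukemia agents only until SL-401 is discontinued. Protocol 9.7 provides for follow-up of patients who go on to SCT.

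**Transplant and MRD.** Protocol 11.2 bases the rule on this premise: "Because no available anti-leukemia therapies (other than allogeneic transplant) are believed to be associated with the eradication of evidence of MRD".

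**Baseline.** Stage 2 entry uses a local result (Protocol 5.2, criterion 5): "For patients enrolling in Stage 2, the bone marrow evaluation determined locally within the previous 6 months indicates the presence of MRD". Protocol 6.2.2 enrolls up to 20 such patients "so that up to 15 patients with evidence of MRD as determined centrally are evaluable for safety and response at this dose". Protocol 8.11 requires a central marrow within 14 days before the first dose, and SAP 3.4 takes the most recent pre-dose measurement as baseline. The mITT definition in SAP 2.1 requires only eligibility and one dose, and SAP 3.2 describes the tested group only as high-risk AML patients enrolled in Stage 2.

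**The concern.** The 5% null is a statement about what happens without an SL-401 effect, on the premise that nothing else the patient receives clears MRD. The plan names one exception, transplant, and then leaves post-transplant marrows inside the numerator. A patient who stops SL-401 while still MRD-positive, is transplanted, and has a negative marrow before Month 12 meets the definition as written.

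The SAP did address later therapy for relapse-free survival. Section 4.3.2 carries follow-up through SCT and censors at other anticancer therapies. The formally tested endpoint has no counterpart.

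The second gap is smaller. Because 4.3.1 does not name the baseline laboratory, a patient who is positive on an older local test and negative on the central baseline marrow is not explicitly excluded from the denominator.

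At stake is the error rate of a rule decided by two events, in an open-label trial whose SAP already reports enrollment at database lock. Any choice left open could be made with the results in view.

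**Working it through.** **Inputs.** From SAP 3.1: null 0.05, alternative 0.20, at least 2 conversions, planned n = 15, and 9 enrolled in Stage 2. The SAP does not restate the rule for 9, so applying the same threshold there is an assumption.

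**1. The plan's own figures.** With X binomial, P(X ≥ 2) = 1 − (1−p)^n − n·p·(1−p)^(n−1).
- n = 15, p = 0.05: 1 − 0.4633 − 0.3658 = 0.171. The stated 17% is reproduced.
- n = 15, p = 0.20: 1 − 0.0352 − 0.1319 = 0.833. The stated power above 80% is reproduced.
- n = 9, p = 0.05: 1 − 0.6302 − 0.2985 = 0.071. At p = 0.20 the power is 0.564.

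**2. One conversion not due to SL-401.** Given one such patient, the rule needs only one more event among the other n − 1 patients at 5%: 1 − 0.95^(n−1).
- n = 15: 1 − 0.95^14 = 1 − 0.4877 = 0.512, against 0.171.
- n = 9: 1 − 0.95^8 = 1 − 0.6634 = 0.337, against 0.071.
- Two such patients: the rule is met with certainty.

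These are conditional on the event having occurred and need no assumed transplant rate.

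**3. How often it could occur.** The documents give no rate. Let q be the share of patients who receive a later therapy multiplied by the share then MRD-negative. Assumed ranges are 5–30% for the first and 30–70% for the second, so q runs from 0.05 × 0.30 = 0.015 to 0.30 × 0.70 = 0.21. With the 5% null added, p = q + (1 − q) × 0.05.

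| | n = 15 | n = 9 |
|---|---|---|
| P(≥2 from these marrows alone) | 0.021 to 0.855 | 0.008 to 0.593 |
| False-positive chance with the 5% null added | 0.250 to 0.919 | 0.110 to 0.698 |
| If such marrows are excluded | 0.171 | 0.071 |
| q at which they alone meet the rule half the time | about 11% | about 18% |

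**4. Baseline laboratory, by reading.** Three places point to a central baseline: SAP 3.1 ties the 15 patients to central MRD, Protocol 8.11 requires the central pre-dose marrow, and SAP 3.4 selects the most recent measurement. Three places do not secure it: SAP 4.3.1 names no laboratory, SAP 3.2 tests those enrolled in Stage 2, and SAP 2.1 labels eligible, dosed patients as evaluable without requiring central positivity.

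**The case against.** The strongest reply is that this is a wording gap in a secondary endpoint, in a study whose primary objectives are dose and safety. The rule is a lenient activity screen written for 15 patients, and 9 were enrolled. Eligibility excludes immediate transplant candidates (Protocol 5.2, criterion 6), which should make early SCT less common. By-patient efficacy listings (SAP 4.3) and subsequent-treatment listings (SAP 4.4.6) would let a reader spot a post-transplant negative marrow. All of this stands and lowers the severity. It does not remove the gap: criterion 6 does not prevent later SCT, and a listing does not change what the formal count includes.

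Three stronger readings are tempting and not supported.

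- **That the plan counts centrally negative patients as converted.** The sections set out in step 4 favor a centrally positive denominator. The fault is that 4.3.1 does not say so.
- **That the plan expects 25% local/central discordance.** The move from 20 to 15 gives 5/20, but 20 is a cap, and the target of evaluable patients also leaves room for inadequate marrows and dropout. Applying 25% to the 15 would contradict the plan, since those 15 are centrally positive by definition.
- **That other new therapy inflates the count as transplant does.** On the plan's own premise, no available therapy except allogeneic transplant is believed to clear MRD. That route is weak and is covered for consistency only.

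**Conclusion.** The concern holds in a limited form. As written, the endpoint credits SL-401 with MRD clearance achieved by transplant, and the baseline laboratory is implied but not stated. The firm result is the sensitivity of the rule: one such conversion takes the false-positive chance from 0.171 to about 0.51 with 15 patients, or from 0.071 to about 0.34 with 9, and two decide the result.

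A reader might infer that these marrows will be enough by themselves to make the study positive. The documents do not support that, because they give neither a transplant rate nor a discordance rate. The range of 2–86% (n = 15) or 1–59% (n = 9) rests entirely on the assumed q of 1.5–21% and shows possibility, not expectation.

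Severity: should-fix. The endpoint is secondary, but it is the only one formally tested.

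**What to change.** Amend SAP 4.3.1 to state:

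- **Denominator:** patients MRD-positive by the central laboratory on the pre-dose baseline marrow.
- **Numerator:** those who are MRD-negative by the central laboratory on a marrow taken before any SCT, including conditioning, or, for consistency, before any other new anti-leukemia therapy.
- **Negative only after such an event:** counted as non-converters.
- **Shown separately:** post-SCT MRD results, and patients who were local-positive but central-negative at baseline.

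The stated 17% error and power above 80% then apply to 15 patients. With 9, the same threshold gives 0.071 and 0.564.

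The cost is mainly wording. Central baseline marrows are already required, and the transplant and new-therapy dates are already needed for RFS. Because SAP 3.1 reports enrollment at database lock, the change should be disclosed as a late clarification, in SAP section 5 and in the study report. The downside is a smaller denominator and possibly a lower observed rate, since a patient transplanted before any follow-up marrow counts as a non-converter.

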4.3.2. Relapse-Free Survival

Relapse-Free Survival is defined as the time from the date of first infusion of Tagraxofusp to the date of relapse (AML recurrence) or death from any cause, whichever occurred first. According to current WHO classification, a myeloblast population comprising greater than 5% of nucleated cells in the bone marrow or blood is required for diagnosis of AML relapse following CR/CRi

(if no peripheral blasts are present, then a confirmation aspirate is required ≥ 1 week subsequent to the aspirate at which $>5\%$ blasts were identified).

For patients who receive SCT, RFS will include time to progressive disease or death post-transplant. Patients who do not progress and are still alive at the time of analysis will be censored on the date of last treatment recorded prior to the analysis cut-off date. If patients start other anticancer therapies (with the exception of SCT or preparations for SCT), they will be censored at the latter of the date of last treatment with Tagraxofusp or date of last disease assessment recorded that occurred prior to the start of the new therapy.

The proportion of subjects receiving treatment who are alive and without evidence of AML recurrence will be presented. The distribution for RFS will be estimated by Kaplan-Meier methodology and the 25th percentile, median, 75th percentile, number and percentage of events and censored observations, and appropriate CIs will be presented. 6- and 12-month RFS rates will be evaluated.

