7.5.2 Dose, Schedule, and Duration of Treatment

Patients will receive SL-401 by IV infusion over 15 minutes for 5 consecutive days (or 5 doses over a period not to exceed 10 days if postponement is required for toxicity) of a 28-day cycle in the absence of disease progression or other withdrawal criteria.

Refer to the Pharmacy Manual for details regarding SL-401 administration.

Patients with evidence of ongoing disease control during treatment (without evidence of clinically significant progressive disease or intolerable toxicity) may receive repeated cycles of

SL-401 even if eradication of MRD, in the judgment of the Investigator, is not attained. Patients can receive up to 6 total cycles of SL-401 as long as there is ongoing evidence of AML remission, as determined by the Investigator. The administration of additional cycles of SL-401 (> 6 cycles) must be discussed with the Medical Monitor at which time the individual patient's potential risk/benefit of further treatment will be assessed.

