8.11 Tumor Assessments

Following determination of eligibility, locally, the following assessments must be performed centrally at baseline (after local determination of eligibility, but prior to receiving investigational treatment on study) within 14 days prior to the first administration of SL-401, and on the following schedules until, in the judgment of the Investigator, there is evidence of relapsed or progressive disease.

8.11.1 Bone Marrow and Peripheral Blood Examinations including Biological/Target/Correlative Studies by Central Laboratory

Bone marrow aspirates (+ biopsy) will be collected within 14 days prior to first administration of SL-401 and 28 (\pm 7) days after the start of Cycles 2, 4 and 6, every 3 months (\pm 1 month) thereafter through 12 months after start of SL-401, and thereafter at the discretion of the Investigator. If the Cycle 2 (Day 28 (\pm 7 day) bone marrow examination is empty (i.e., hypocellular) or inadequate, a bone marrow examination should be repeated in 14 (\pm 7) days to document response. If additional time is required to complete the repeat examination,

consult with the Medical Monitor. The Cycle 2, 4 or 6, Day 28 (\pm 7 days) bone marrow assessment should occur on Day 28 (\pm 7 days) even in the setting of patients receiving SL-401 over 6-10 days (as opposed to 5 consecutive days).

For adequate MRD assessment, it is critical that the first aspirate from each bone marrow collection: 1) consists of 2 mL of BM aspirate in its entirety; and 2) be shipped in its entirety via priority overnight to the central processing laboratory ([REDACTED], Attn: [REDACTED] [REDACTED]), as described in the Laboratory Manual. Additional bone marrow may be used for local assessment at the Investigator's discretion.

Results of bone marrow examinations will be provided to the Investigator by the central laboratory within 1 week of sample receipt.

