11.5.2 Relapse (progression) – free Survival (RFS/PFS)

Relapse-free survival is defined as the proportion of patients who remain free of AML recurrence (hematologic) and alive. According to current WHO classification, a myeloblast population comprising greater than 5% of nucleated cells in the bone marrow or blood is required for diagnosis of AML relapse following CR/CRi (if no peripheral blasts are present, then a confirmation aspirate is required ≥ 1 week subsequent to the aspirate at which $>5\%$ blasts were identified). RFS will be evaluated via Kaplan-Meier analysis (in which patients who are lost to follow-up or who are not evaluable for recurrence have data censored), and via direct proportional analysis (percentage of patients receiving treatment [or treatment at MTD or otherwise derived Stage 2 dose] who are alive and without evidence of AML recurrence). Median, 6- and 12-month RFS rates will be evaluated.

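### SAP 4.3.2 censors relapse-free patients at their last treatment while later relapses and deaths still count, so the Kaplan-Meier RFS is biased downward, mainly at 12 months

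*SAP*

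**What the plan says.** SAP 4.3.2 measures RFS from first infusion to "date of relapse (AML recurrence) or death from any cause, whichever occurred first", with no limit to the treatment period. For patients without an event it says: "Patients who do not progress and are still alive at the time of analysis will be censored on the date of last treatment recorded" before the analysis cut-off. The next sentence has a different rule for patients who start other anticancer therapy: "they will be censored at the latter of the date of last treatment with Tagraxofusp or date of last disease assessment recorded". The section also states that "6- and 12-month RFS rates will be evaluated".

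SAP 4.3.3 censors OS at the last date the patient was known to be alive.

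Protocol 11.5.2 describes a Kaplan-Meier analysis "in which patients who are lost to follow-up or who are not evaluable for recurrence have data censored". It says who is censored but gives no date. SAP Section 5 declares no changes from the protocol's analyses.

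On treatment length, Protocol 7.5.2 says: "Patients can receive up to 6 total cycles of SL-401 as long as there is ongoing evidence of AML remission". Further cycles need discussion with the Medical Monitor. On follow-up, Protocol 8.11.1 schedules marrows every 3 months "thereafter through 12 months after start of SL-401, and thereafter at the discretion of the Investigator". Section 7.6.2 continues tumor assessments after treatment stops, until relapse or progression.

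**The concern.** Kaplan-Meier estimation needs censoring that carries no information about later failure. Here the date on which a patient leaves the risk set is decided by what happens afterwards. A patient who finishes six cycles and relapses at month 9 is at risk for nine months. A patient who finishes six cycles and is in documented remission at month 12 is at risk for less than five. After the last dose, the risk set holds only patients who will fail before the cut-off.

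RFS is a named secondary objective, and both planned landmarks fall after the usual last dose. The same rule feeds the RFS quartiles and the RFS curves by MRD status and line of therapy. Patients who do well lose the follow-up that shows it, while those who switch to other therapy keep credit for assessments after their last dose.

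**Working it through.** The documents state no RFS rate, event count or RFS power, so there is no planned figure to reproduce.

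**Last dose.** Cycles last 28 days, with dosing on Days 1 to 5, or to Day 10 at the latest (Protocol 7.5.2). The sixth cycle's last dose falls on Day 5 × 28 + 5 = 145, or 5 × 28 + 10 = 150, that is 4.7 to 4.9 months. It is earlier if the patient stops, and later with cycle delays or extra cycles.

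**Direction.** The two rules share the same events at the same times. For any patient whose last assessment is no earlier than the last dose, the SAP rule ends time at risk sooner or on the same day. Each Kaplan-Meier factor 1 − d/n then has the same d and an equal or smaller n, so the estimate cannot be higher.

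**Nine-patient illustration** (nine is the Stage 2 enrollment in SAP 3.1; the event times are invented). Relapses occur at 3, 5.5, 8 and 11 months; five patients are relapse-free past month 12; all receive six cycles.
- Censoring at last assessment: 6 months = 8/9 × 7/8 = 77.8%; 12 months = 5/9 = 55.6%.
- SAP rule: after month 3 the estimate is 8/9. The five relapse-free patients then leave, so three remain at 5.5 months. 6 months = 8/9 × 2/3 = 59.3%. At 8 months the factor is 1/2 and at 11 months it is 0, so 12 months = 0%.

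**General formula.** Let c be the last-dose time, S(t) the true RFS and q the share of patients event-free at the cut-off. Up to c everyone event-free is at risk. After c, the share at risk is S(t) − q. For t between c and the shortest follow-up:

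KM(t) = S(c) × [S(t) − q] / [S(c) − q]

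**Assumptions, none of them trial figures.**
- RFS is exponential, everyone receives six cycles, and c = 145/365.25 years.
- The 12-month event rate is 60% or 30%. Protocol 3.1.3 gives one-year relapse above 60% with MRD and below 30% without it, but for intermediate-risk patients after two induction cycles, and for relapse alone. They serve only as two test values.
- Follow-up is either exactly 12 months, or uniform over 12 to 36 months. The latter follows from 24 months of enrollment within about 36 months (Protocol 6.3).

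For uniform follow-up, q = [S(1) − S(3)]/(2λ), with t in years and λ = −ln(1 − event rate).
- 60%: λ = 0.9163; S(c) = 0.695; q = (0.400 − 0.064)/1.8326 = 0.183. KM at 12 months = 0.695 × 0.217/0.512 = 0.294.
- 30%: λ = 0.3567; S(c) = 0.868; q = (0.700 − 0.343)/0.7133 = 0.500. KM at 12 months = 0.868 × 0.1995/0.3675 = 0.471.

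For exactly 12 months' follow-up, q = S(1), so KM at 12 months is 0.

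| Event rate | Follow-up (months) | 6-month true | 6-month SAP rule | 12-month true | 12-month SAP rule |
|---|---|---|---|---|---|
| 60% | 12–36 | 63.2% | 61.0% | 40% | 29.4% |
| 60% | 12 | 63.2% | 54.8% | 40% | 0% |
| 30% | 12–36 | 83.7% | 79.4% | 70% | 47.1% |
| 30% | 12 | 83.7% | 70.6% | 70% | 0% |

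Fixed follow-up of 18 and 24 months gives 12-month readings of 23% and 31% (true 40%), and 35% and 48% (true 70%). A simulation of 400,000 patients with 12 to 36 months' follow-up agrees with the formula (29.5% and 47.0%).

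**Early stopping.** In simulations with n = 9 or 27, median RFS of 6, 12 or 24 months and a 0%, 25% or 50% chance of stopping per cycle, the mean 6-month bias was 1 to 13 points with 12–36 months' follow-up and 6 to 30 points with 12 months. The 12-month bias was 6 to 29 and 24 to 71 points. In the limit where everyone stops after Cycle 1 (c = 5 days), the formula gives a 6-month reading of 46.1% against 83.7% (30% event rate, 12 months' follow-up), a gap of about 38 points.

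**The case against.** Several points on the other side have force.

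- **The 0% result is an edge case.** It needs everyone to be followed for exactly 12 months. The planned enrollment and duration imply longer follow-up for most patients, and the bias shrinks as more failures are observed. This stands.
- **Six months is not twelve.** A reader might infer that both landmarks are sharply biased. With six cycles for all and 12 to 36 months' follow-up, the 6-month loss is only 2 to 4 points. It becomes large only with early stopping, short follow-up or both.
- **Day 145 to 150 is not a ceiling.** Protocol 7.5.5.10.1 allows delayed cycle starts, and 7.6.1 allows more than six cycles in sustained remission, which concerns the very patients being censored. Both reduce the bias.
- **RFS is not lost.** A reader might infer that the endpoint cannot be read, or that follow-up stops early. It is the censoring date that is early; assessments continue. Both documents also plan the crude proportion alive without recurrence, and SAP 4.3 plans by-patient listings.
- **The SAP does not contradict the protocol.** Protocol 11.5.2 gives no censoring date, so the SAP fills a gap. The conflict is within the SAP.
- **The wording may be a slip.** The sentence names no drug, and assessment may have been meant. The next sentence, which names Tagraxofusp, makes the last SL-401 dose the natural reading, and nothing elsewhere corrects it.

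RFS is also descriptive in a single-arm study whose primary objectives are dose and safety. That limits the consequences but does not make the estimate right.

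**Conclusion.** The concern holds in this form. As written, the rule is outcome-dependent censoring. The direction is certain for patients followed beyond their last dose: the RFS curve can only be equal or lower. The rule is also inconsistent with the sentence that follows it and with the OS rule.

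The size is conditional on the exponential model, the assumed event rates and six cycles for all. With 12 to 36 months' follow-up, the 12-month estimate loses about 11 points from a true 40% and about 23 from a true 70%. The 6-month loss should be quoted as a range: 2 to 4 points with that follow-up, 8 to 13 with 12 months, and 30 or more in the worst early-stopping cases. Actual follow-up and cycles received are not in the documents, so the bias in the final tables cannot be stated.

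If no event follows the last censoring, the curve stays flat with nobody at risk, and the landmark is not estimable rather than low. OS and the crude proportion are not affected.

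**What to change.** Replace the censoring sentence in SAP 4.3.2 with:

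*Patients alive without documented relapse at the analysis cut-off are censored at the date of their last adequate disease assessment on or before the cut-off.*

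Define an adequate assessment (for example, a marrow, or a peripheral blood differential, sufficient to show no relapse). State a convention for patients with no post-baseline assessment; Day 1 is a common choice, though the documents supply none. Record the rule and the reason for it in SAP Section 5, which now declares no changes. The SAP already reports enrollment at database lock, so date the entry and make it before the final RFS tables are produced.

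The cost is one sentence, a short definition and one line of derivation code. The assessment dates are already collected under the schedule of events.
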